Hematologic	
Grade 4 neutropenia (<500/mm³) lasting ≥5 days or complicated by infectionGrade ≥ 3 documented infection with neutropenia.Grade ≥ 3 febrile neutropenia (ANC<1000/mm³ complicated by fever ≥38.3 °C or 101°F° C or a sustained temperature of ≥38.0C (100.4 ° F) for more than 1 hour.Grade 3 thrombocytopenia (≥ 25,000/mm³ and <50,000/mm³) associated with bleeding or requiring platelet transfusion.Grade 4 thrombocytopenia (<25,000/mm³). Grade 4 anaemia (i.e., life-threatening consequences or urgent intervention indicated).

Table 5.2.6.1: 1 Dose Limiting Toxicities
(according to CTCAE V5.0) (cont'd)

Drug related toxicity category	Criteria defining a DLT*
Non-hematologic	Non-laboratory toxicity 
Any Grade 4 or 5 AE other than disease progression.Any Grade 2 drug-related uveitis or eye pain or blurred vision that does not respond to topical therapy and

		
does not improve to Grade 1 severity within 2 weeks or requires systemic treatment.
 
• Any treatment-related Grade ≥ 2 toxicity that occurred during Cycle 1 that persists and results in an inability to administer BI 754091 or BI 836880 on Cycle 2 Day 1.• any grade ≥ 2 pneumonitis of any duration• Any toxicity Grade ≥ 3 toxicity except:
○ Grade 3 immune-related AE that resolves to \leq Grade 1 or to baseline with immunosuppressive therapy within 2 weeks○ Grade 3 asymptomatic endocrine disorders (thyroid, pituitary, and/or adrenal insufficiency) that are managed with or without systemic corticosteroid therapy and/or hormone replacement therapy.○ Grade 3 or 4 elevation in serum amylase and/or lipase that is not associated with clinical or radiographic evidence of pancreatitis○ Grade 3 nausea or vomiting that lasts <48 hours, and resolves to \leq Grade 1 either spontaneously or with conventional medical intervention○ Alopecia○ Grade 3 fatigue that persists less than 7 days○ Grade 3 infusion related reaction which can be controlled by appropriate medication according to investigator's decision, and the subsequent infusion will not be delayed for more than two weeks.○ Grade 3 rash that resolves to \leq Grade 1 within 2 weeks○ Grade 3 endocrine disorders (thyroid, pituitary, and/or adrenal insufficiency) that are managed with or without systemic corticosteroid therapy and/or hormone replacement therapy, and the patient is asymptomatic.○ Grade 3 tumour flare.

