	
In the dose expansion study, only dose reductions are allowed for BI 836880.
 
Table 4.1.4: 3 Dose reduction recommendations for BI 836880 in Part 2
 

BI 836880 received dose	BI 836880 reduced dose	

720 mg	480 mg	

 
A dose reduction of BI 836880 from 720 mg to 480 mg is allowed, if investigator can attribute the AE unequivocally to the BI 836880 (for eg., hypertension). If the reduced dose is still intolerable, the dose maybe delayed (please see below the sub-section “Delay of treatment”). Where deemed in the best interest of the patient, the investigator may restart at the originally assigned dose of 720 mg of BI 836880 as soon as deemed clinically appropriate.
 
Delay of Treatment:
 
During combination therapy, if treatment is held or discontinued due to an AE(s), both BI 836880 and BI 754091 will be held or discontinued together. If treatment is to be restarted after resolution (\leq Grade 1 or baseline) of the AE, both BI 836880 and BI 754091 must be started together. The combination therapy may be delayed for up to 6 weeks because of AEs, following discussion with the sponsor.
	BI 836880 received dose	BI 836880 reduced dose	720 mg	480 mg
BI 836880 received dose	BI 836880 reduced dose				
720 mg	480 mg				
Rationale for change	Changes refer to the possibility to down dithrate the dose for the patients in case of AEs.				
Section to be changed	4.2.2 Restrictions				
Description of change	
Changed from:
 
Concomitant anti-cancer therapy is not allowed. Radiotherapy for local symptom control of non-target lesions can be allowed after consulting the investigator and sponsor. 
To:
 
Concomitant anti-cancer therapy is not allowed. Radiotherapy for local symptom control of non-target lesions can be allowed after consulting the investigator and sponsor. Palliative radiotherapy will not be allowed during the first cycle for any lesion. Palliative radiotherapy is allowed only for non-target lesions, following discussion with the Medical Monitor, provided that the reason for radiotherapy does not reflect PD and does not interfere with response assessment. Lesions that have been exposed to radiotherapy are no longer evaluable, and may not be included in the assessment of the non-target lesions and the overall assessment. Unless in emergency
				

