	
If symptoms of an infusion-related reaction CTCAE grade 2 or higher, the infusion should be temporarily stopped. The intensity and prolongation of vital sign monitoring should be considered. Upon recovery, the study drug should be infused at 50% of the rate at which the reaction occurred. Depending on the time of occurrence and the severity of the reaction, the investigator may consider administering additional supportive medication, e.g. corticosteroids for re-introduction. Infusion rate and premedication for further treatment cycles should be adapted according to Investigator decision, but adaption of administration scheme need to be agreed with sponsor.
 
To:
 
The expected infusion time is 60 minutes for BI 754091 and same for BI 836880; BI 754091 will be administered first, then 15 minutes (+/- 10 min) after the end of this infusion BI 836880 will be administered.
 
In case of technical issues or complications during infusion, the total infusion time (including stop time and flushing) for BI836880 should not exceed 360 minutes.
 
For BI 754091, in case of technical issues or complications during infusion, the total infusion time (including stop time) should not exceed 180 minutes.
 
Appropriate drugs and medical equipment to treat anaphylactic reactions must be immediately available, and study personnel must be trained to recognize and treat anaphylaxis.
 
In the event of an infusion-related reaction \leq Grade 2, the infusion rate of BI 754091 may be decreased by 50% or interrupted until resolution of the event and re-initiated at 50% of the initial rate until completion of the infusion. In patients experiencing infusion-related reactions \leq Grade 2, subsequent infusions may be administered at 50% of the initial rate. Depending on the time of occurrence and the severity of the reaction, the investigator may consider administering additional supportive medication, e.g. corticosteroids for re-introduction. Infusion rate and premedication for further treatment cycles should be adapted according to Investigator decision, but adaption of administration scheme need to be agreed with sponsor. If an infusion related reaction is Grade 3 or higher in severity at any point during the study, treatment with BI 754091 has to be permanently discontinued.
 
Adding of:

--	---

	Rescreening is generally not allowed. In individual cases, rescreening can be considered in alliance with the sponsor.

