Rationale for change	Change of the administration time for BI 836880 and adding of wording regarding the new available information for infusion related reaction in line with the new wording for Appendix 10.4 . Adding for wording regarding rescreening of patients.
Section to be changed	4.2.2. Restrictions
Description of change	Adding of wordin G: ...For patients in the cohort D (Glioblastoma) higher doses of corticosteroids may be allowed as defined in the cohort-specific eligibility criteria.
Rationale for change	Adding to use higher corticosteroids for Cohort D Glioblastoma patient-
Section to be changed	5.1 Assessment of efficacy
Description of change	
Change from: ...
 
Efficacy endpoints will be assessed every 2 cycles (6 weeks) as specified in the FC. An additional evaluation at EoT is only applicable; when patient has no PD documented, will not continue with regular imaging in Follow-up period and did not have imaging within the last 4 weeks before EoT. At Safety Follow-up visit, in case a patient has discontinued due to PD one additional tumor assessment should be done in case no other cancer treatment has been initiated. All measurements must be recorded in metric notation.
 
All tumor imaging performed in this trial will be collected by authorized CRO and stored until shipment to Boehringer Ingelheim. The CRO will not be implicated in tumor response evaluation. This collected data may be considered for central review at a later time point.
 
To:
 
Efficacy endpoints will be assessed every 2 cycles (6 weeks) as specified in the FC. An additional evaluation at EoT is only applicable; when patient has no PD documented, will not continue with regular imaging in Follow-up period and did not have imaging within the last 4 weeks before EoT. In case a patient has discontinued due to PD one additional tumor assessment should be done according to iRECIST in case no other cancer treatment has been initiated (confirming image should be done 4 – 6 weeks after the last image). For Glioblastoma patients, an additional image according to iRANO should be taken 3 month after PD. All measurements must be recorded in metric notation.

	
All tumor imaging performed in this trial will be collected by authorized CRO and stored until shipment to Boehringer Ingelheim. The CRO will not be implicated in tumor response evaluation. This collected data might be considered for central review at a later time point.

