	
initial rate until completion of the infusion. In patients experiencing infusion related reactions \leq Grade 2, subsequent infusions may be administered at 50% of the initial rate.
 
If a patient experiences an infusion-related reaction, acetaminophen and/or an antihistamine (e.g., diphenhydramine) and/or corticosteroid or equivalent medication per institutional standard may be administered prior to subsequent infusions at the discretion of the Investigator for secondary prophylaxis of infusion-related reactions. If an infusion-related reaction is Grade 3 or higher in severity at any point during the study, treatment with BI 836880 or BI 754091 will be permanently discontinued.

Rationale for change	Adapted wording because of new program related information.
Section to be changed	5.2.7.2 Adverse event collection and reporting
Description of change	
Change from:
 
...
 
AE reporting to sponsor and timelines
 
The investigator must report SAEs, AESIs, and non-serious AEs which are relevant for the reported SAE or AESI, on the BI SAE form immediately (within 24 hours) to the sponsor's unique entry point (country specific reporting process will be provided in the ISF). The same timeline applies if follow-up information becomes available. In specific occasions the investigator could inform the sponsor upfront via telephone. This does not replace the requirement to complete and fax the BI SAE form.
 
With receipt of any further information to these events, a follow-up SAE form has to be provided. For follow-up information the same rules and timeline apply as for initial information.
 
To:
 
AE reporting to sponsor and timelines
 
The investigator must report SAEs, AESIs, and non-serious AEs which are relevant for the reported SAE or AESI, on the BI SAE form immediately (within 24 hours) to the sponsor's unique entry point (country specific reporting process will be provided in the ISF). The same timeline applies if follow-up information becomes available. In specific occasions, the investigator could inform the sponsor upfront via telephone. This does not replace the requirement to complete and send the BI SAE form.

Rationale for change	Adaption needed as of new distribution possibilities in some countries.
Section to be changed	5.4 Assessment of Biomarkers
Description of change	
Rationale for change	Wording needed to be adapted for the use of radiomics
Section to be changed	

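### Amendment 5 names different drugs in two permanent-stop rules for a Grade 3 or higher infusion reaction, and neither fits the Part 2 rule that both drugs stop together

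*Protocol*

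**What the plan says.** Four provisions of the Protocol bear on this. BI 754091 is ezabenlimab from Amendment 6 onwards.

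- **Section 4.1.4, Global Amendment 5, new text.** BI 754091 is infused first and BI 836880 follows. For a reaction of Grade 2 or below, "the infusion rate of BI 754091 may be decreased by 50% or interrupted until resolution of the event". If the reaction reaches Grade 3 or higher "at any point during the study, treatment with BI 754091 has to be permanently discontinued". BI 836880 appears in neither sentence. The stated reason is to bring in new information on "infusion related reaction in line with the new wording for Appendix 10.4".
- **Infusion-related reactions, Global Amendment 5, new text.** The section field of this log entry is blank; cross-references in Sections 3.1 and 6.1 (Amendment 4) identify it as 5.2.7.1. For Grade 2 or below, the rate may be reduced for either drug. If the reaction is "Grade 3 or higher in severity at any point during the study, treatment with BI 836880 or BI 754091 will be permanently discontinued".
- **Section 4.1.4, Delay of Treatment, Part 2, Global Amendment 4.** When an adverse event leads to a hold or a stop, "both BI 836880 and BI 754091 will be held or discontinued together". After resolution they must be restarted together.
- **Section 4.1.4, Global Amendment 6.** In some cases, after discussion with the sponsor, one drug may continue where the event is clearly attributed to the other and calls for a temporary stop of that other drug.

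**The concern.** Both Grade 3 rules are new text of the same amendment, so this is not a comparison of old wording with new. They require a permanent stop but do not name the same drug, and neither says what part attribution plays. Infusion reactions are a recognised risk of both antibodies, and all of them are adverse events of special interest. At stake is patient safety and consistent conduct: two sites that follow different sections could handle the same Grade 3 reaction to BI 836880 differently, and both could point to the protocol.

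**Working it through.** No sample size, power or error rate is involved. The check is a side-by-side reading of the rules, followed by one small calculation on timing.

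**Step 1. What each rule instructs**

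| Provision | Grade 2 or below | Grade 3 or above | Attribution |
|---|---|---|---|
| 4.1.4 (Amendment 5) | rate change for BI 754091 | permanent stop of BI 754091; silent on BI 836880 | not stated |
| 5.2.7.1 (Amendment 5) | rate change for either drug | permanent stop of one drug or the other, not specified | not stated |
| 4.1.4 Delay of Treatment, Part 2 (Amendment 4) | any adverse event leading to a hold or stop | both held or both stopped; joint restart possible | not stated |
| 4.1.4 (Amendment 6) | not grade-specific | one drug may continue while the other is stopped temporarily | must be clear, with sponsor discussion |

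The mismatch between the first two rows runs through both grade bands. It is mild for Grade 2 or below, where the rate change is optional. It matters for Grade 3, where the stop is mandatory and permanent.

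**Step 2. Apply the rules to a Part 2 patient with a Grade 3 reaction**

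- *Reaction to BI 754091.* Stopping BI 754091 satisfies both Amendment 5 sentences. They agree on that drug, but neither carries the joint rule's consequence for BI 836880.
- *Reaction to BI 836880.* Taken literally, 4.1.4 stops BI 754091 and gives no instruction for BI 836880. Section 5.2.7.1 stops one of the two without saying which. The delay rule holds or stops both. That is three different instructions.
- *Does Amendment 6 settle it?* No. It covers a temporary stop after discussion with the sponsor, whereas the Amendment 5 sentences require a permanent one.

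**Step 3. How clear would attribution be?**

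Inputs: an expected infusion time of 60 minutes per drug and a gap of 15 ± 10 minutes (4.1.4, Amendment 5); reactions typically 30 minutes to two hours after the start of an infusion, possibly delayed up to 24 hours (6.1, Amendment 4).

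- Start of BI 836880, counted from the start of BI 754091: 60 + 15 = 75 minutes (60 + 5 = 65 to 60 + 25 = 85).
- End of the typical reaction window for BI 754091: 120 minutes.
- Time during the BI 836880 infusion in which a typical BI 754091 reaction could still appear: 120 − 75 = 45 minutes (120 − 85 = 35 to 120 − 65 = 55).

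So for about 45 of the 60 minutes of the second infusion, timing alone does not separate the two drugs. A delayed reaction is harder still to attribute.

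**The case against.** The strongest reply is that 4.1.4 is simply the rule for reactions to BI 754091: its grade-specific sentences name only that drug. Section 5.2.7.1 covers both drugs, and Sections 3.1 and 6.1 send sites there for infusion reactions. On that reading 4.1.4 leaves no protocol-wide gap. The rules are also not strictly incompatible, since stopping both drugs permanently breaches none of them. Much of this stands. But 4.1.4 does not limit its scope, and 5.2.7.1 still does not say which drug its alternative refers to.

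Four stronger readings are tempting, and the documents do not support them.

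- A reader might infer that 4.1.4 stops BI 754091 whatever the cause, so that the causative drug is continued alone. The text says nothing about cause. The joint rule and the Amendment 6 allowance both point against that outcome.
- A reader might take the dose-limiting-toxicity exception, "Grade 3 infusion related reaction which can be controlled by appropriate medication", as a further instruction to re-infuse. It is part of a definition and instructs nothing. Amendment 4 also states that dose-limiting toxicities no longer apply in Part 2.
- A reader might multiply the planned Part 2 size by the 53-cycle limit to gauge exposure. Recruitment ended with the decision of December 2021, so from here only patients still on treatment are affected. No frequency of Grade 3 reactions is given.
- A reader might expect the Part 2 endpoints to shift. Any of these permanent stops is a discontinuation of trial drug, and Part 2 analyses use the treated set (7.3, Amendment 4), so no patient leaves the response analysis on this ground.

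**Conclusion.** The rules are wrong as written. Two mandatory stopping rules from one amendment name different drugs, and neither fits the Part 2 rule that both drugs are held or stopped together. The gap is narrow: essentially a Grade 3 reaction to BI 836880, or one whose cause is unclear. Grade 4 drug-related events already have their own withdrawal rule in 3.3.4.1. Within that gap there are up to three different instructions for one event. The consequence is for safety and consistent handling, with little effect on the analysis.

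Confidence is moderate. The part of the Protocol at hand is the amendment log; the current body text of 4.1.4, 5.2.7.1 and Appendix 10.4 is not shown. Amendment 5 rewrote Appendix 10.4 completely, and that appendix might clarify the intent. The entries shown for Amendments 6 to 8 do not list a revision of either sentence, though Amendments 6 and 7 mention unspecified editorial changes.

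**What to change.** Check the current text of 4.1.4, 5.2.7.1 and Appendix 10.4. Then reconcile the two Amendment 5 rules with each other, with the Part 2 joint-discontinuation and restart rule, and with the Amendment 6 one-drug allowance. The result should state, for a reaction of Grade 3 or higher, one action for each drug, whether it depends on attribution, and what applies when attribution is unclear. The sentences for Grade 2 or below should be aligned in the same way, or 4.1.4 should refer to 5.2.7.1. Which action is right is for the sponsor's safety team. Sites with patients still on treatment should be told.

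The cost is protocol wording and a site letter. No visits, procedures or analyses are added.
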